5.6.4 Management and Surveillance of Listeria During Study Participation

A subject who experiences a fever (CTCAE Grade 1 or greater) 24 hours following the completion of ADXS11-001 infusion should be started on NSAIDs, hydration and other appropriate measures to treat the fever. In the event that the fever persists or worsens 48 hours following the completion of ADXS11-001 infusion then oral or broad spectrum IV antibiotics should be considered based on the subject's medical condition. If the fever remains unresponsive to oral/IV antibiotics 72 hours following the completion of the infusion then a blood culture should be obtained to evaluate for listeremia and determine the appropriate treatment course for the subject.

All subjects will receive a 6 month course of an oral antibiotic regimen as a prophylactic measure approximately 72 hours following the completion of the last dose of ADXS11-001 treatment or at the time of study discontinuation. This additional safety measure is intended to eradicate *Lm* from the body.

Lm surveillance monitoring will also be initiated following the completion of the last dose of ADXS11-001 treatment or at the time of study discontinuation. This monitoring will include obtaining a blood sample for CBC, CMP, including CRP and ESR, and blood cultures for the detection of listeria. Testing will be performed on all subjects who have received at least one dose of ADXS11-001 and occur every 4 months (± 2 weeks) for 3 years.

Should a diagnosis of listeriosis occur at any point after treatment with ADXS11-001 is completed immediate, intensive IV antibiotic treatment (e.g. Ampicillin +/- Gentamicin or other IV antibiotic regimen as indicated) is required. An infectious disease consult should be obtained. Based on each individual subject's case and at the discretion of the treating physician, the removal of any foreign medical object that has been present since treatment with ADXS11-001 was initiated may be warranted. It is extremely important that the investigator, his/her research staff, other healthcare providers involved in the care of the subject as well as each subject participating in this study are educated and made aware of the signs and symptoms of listeriosis and the potential for delayed listeremia/listeriosis. Educational materials for the investigator, research staff, health care providers and patients will be prepared and educational training performed.

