⁸ All Subjects will receive a 7-day course of oral antibiotic therapy starting approximately 72 hours after administration of ADXS11-001. All subjects will also receive an additional 6 month oral antibiotic course to be initiated approximately 72 hours following the last dose of study treatment or anytime upon discontinuation of study treatment.

⁹ Adverse events and serious adverse events will be assessed from the time Informed Consent is obtained through 30 days after the last ADXS11-001 infusion is administered.

¹⁰ Height will be measured at screening only. Monitor vital signs immediately [REDACTED] for the first 4 hours following the completion of every ADXS11-001 infusion.

¹¹ CID1 Safety labs do not need to be repeated if screening labs are collected within 3 days of dosing. All laboratory procedures are to be completed and assessed by the investigator within 3 days prior to the administration of ADXS11-001 to confirm lab criteria for study treatment are met.

¹² Urine pregnancy tests must be performed within 72 hours prior to each ADXS11-001 infusion for female subjects of childbearing potential. If the urine test is positive or cannot be confirmed as negative, a serum pregnancy test will be required.

¹³ *Lm* Surveillance Monitoring will include a 6-month course of oral antibiotics and routine monitoring of CBC, CMP (including CRP, ESR) and blood cultures. Following completion of the last dose of study treatment or following study discontinuation, all assessments will be performed every 4 months (±2 weeks) for 3 years.

¹⁴ Baseline tumor imaging and assessments must be performed within 28 days prior to the first ADXS11-001 infusion in the first study cycle. Subsequent tumor imaging and assessments will be conducted at Week 8 (±1 week) for the duration of study participation. Radiologic progression, not accompanied by clinical deterioration, should be confirmed ≥4 weeks later.

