7.1.2 Clinical Procedures/Assessments

7.1.2.1 Adverse/Serious Adverse Event Monitoring

The investigator or qualified designee will assess each subject to evaluate for potential new or worsening serious events from the time written informed consent is obtained through 30 days after the last ADXS11-001 dose is administered. Adverse experiences. Serious events experienced during this time will be graded, reported and recorded on the eCRF according to NCI CTCAE v 4.0 ([Section 12.2](#)). Toxicities will be characterized in terms regarding seriousness, causality, toxicity grading, and action taken with regard to trial treatment.

Please refer to [Section 7.2](#) for detailed information regarding the assessment and recording of AEs.

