7.1.3.1 Laboratory Safety Evaluations

Laboratory tests for hematology, chemistry, urinalysis, *Lm* surveillance and others are specified in [Table 8](#).

Subjects must meet all lab criteria prior to dosing. Laboratory tests can be performed no more than 3 days prior to dosing. If screening laboratory tests are performed within 3 days prior to initial study treatment, they can be used for C1D1 labs. Results must be reviewed by the investigator or qualified designee and found to be acceptable prior to each dose of trial treatment.

Table 8 Laboratory Tests

Hematology	Chemistry	Urinalysis	Other
Hematocrit	Albumin	Blood	Serum β -human chorionic gonadotropin†
Hemoglobin	Alkaline phosphatase	Glucose	(β -hCG)†
Platelet count	Alanine aminotransferase (ALT)	Protein	PT (INR)
WBC (total and differential)	Aspartate aminotransferase (AST)	Specific gravity	aPTT
Red Blood Cell Count	Lactate dehydrogenase (LDH)	Microscopic exam (If abnormal)	Lm surveillance* blood cultures
Absolute Neutrophil Count	Carbon Dioxide ‡ (CO₂ or bicarbonate)	Urine pregnancy test †	
	Calcium		
	Chloride		
	Creatinine		
	C-Reactive Protein (CRP)*		
	Erythrocyte Sedimentation Rate (ESR)*		
	Glucose		
	Potassium		
	Sodium		
	Total Bilirubin		
	Direct Bilirubin (If total bilirubin is elevated above the upper limit of normal)		
	Total protein		
	Blood Urea Nitrogen		

† Perform on women of childbearing potential only. If urine pregnancy results cannot be confirmed as negative, a serum pregnancy test will be required.

‡ If considered standard of care in your region.

**Lm* surveillance Monitoring will include routine monitoring of CBC, CMP (including CRP, ESR) and blood cultures. Following completion of study treatment all assessments will be performed every 4 months (± 2 weeks) for 3 years.

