7.2 Assessing and Recording Adverse Events

An AE is defined as any untoward medical occurrence in a patient or clinical investigation subject administered a pharmaceutical product and which does not necessarily have to have a causal relationship with this treatment. An AE can therefore be any unfavorable and unintended sign (including an abnormal laboratory finding, for example), symptom, or disease temporally associated with the use of a medicinal product or protocol-specified procedure, whether or not considered related to the medicinal product or protocol-specified procedure. Any worsening (i.e., any clinically significant

adverse change in frequency and/or intensity) of a preexisting condition that is temporally associated with the use of the Sponsor's product, is also an AE.

Changes resulting from normal growth and development that do not vary significantly in frequency or severity from expected levels are not to be considered AEs. Examples of this may include, but are not limited to, onset of menses or menopause occurring at a physiologically appropriate time.

The Sponsor's product includes any pharmaceutical product, biological product, device, diagnostic agent or protocol-specified procedure, whether investigational (including placebo or active comparator medication) or marketed, manufactured by, licensed by, provided by or distributed by Advaxis for human use.

AEs may occur during the course of the use of Advaxis' product in clinical trials or within the follow-up period specified by the protocol, or prescribed in clinical practice, from overdose (whether accidental or intentional), from abuse and from withdrawal.

AEs may also occur in screened subjects during any pre-allocation baseline period as a result of a protocol-specified intervention, including washout or discontinuation of usual therapy, diet, placebo treatment or a procedure.

All AEs will be recorded from the time the consent form is signed through 30 days following cessation of treatment on the Adverse Event CRF forms/worksheets. The reporting timeframe for AEs meeting any serious criteria is described in [Section 7.2.3.1](#).

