8.5 Analysis of Safety Data

All AEs will be summarized by patient, treatment, and prior recurrence history (aggressive [recurrence within 2 years]/non-aggressive).

The NCI CTCAE v 4.0 will be used for AE grading (Grades 1 to 4). AEs will be classified using the Medical Dictionary for Regulatory Activities (MedDRA®) coding system.

The overall incidence of AEs will be summarized and classified by body system and by treatment group. An AE will be summarized if the onset date occurs anytime during study treatment or up to 30 days after the last dose of study treatment; or, if it occurs prior to Day 1 and worsens while on therapy. The type, incidence, severity, and causality of each AE, the duration of the event, and any required treatment interventions will be tabulated.

Physical examination results will be presented in the patient data listings. Vital sign measurements will be summarized at each infusion using descriptive statistics. The incidence of clinically significant laboratory abnormalities will be presented, and laboratory data will be summarized at each infusion by the NCI CTCAE v 4.0 toxicity grades. Laboratory data will be presented for patients having Grade 3 or 4 changes from baseline.

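### AE recording and the Section 8.5 AE summaries stop 30 days after the last dose, so delayed listeriosis, the target of 3 years of Lm surveillance, is left out of the AE tables

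*Combined protocol and SAP*

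**What the plan says.** The criteria for evaluation in Section 1 list Lm surveillance monitoring under safety, beside AEs and laboratory evaluations. Section 4.2.2 is devoted to delayed infection. Section 5.6.4 starts surveillance after the last dose or at discontinuation, for everyone who received at least one dose: "This monitoring will include obtaining a blood sample for CBC, CMP, including CRP and ESR, and blood cultures for the detection of listeria". The interval is 4 months (±2 weeks) and the duration 3 years; Section 7.1.6.3 repeats this and counts from the last dose.

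Three sections set the collection window for adverse events:

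- Section 6.1, footnote 9: "Adverse events and serious adverse events will be assessed from the time Informed Consent is obtained through 30 days after the last ADXS11-001 infusion".
- Section 7.1.2.1: events are assessed "from the time written informed consent is obtained through 30 days after the last ADXS11-001 dose is administered".
- Section 7.2: "All AEs will be recorded from the time the consent form is signed through 30 days following cessation of treatment".

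Section 8.5 sets the reporting window. An AE is summarised if its "onset date occurs anytime during study treatment or up to 30 days after the last dose of study treatment", or if it began before Day 1 and worsened on therapy.

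Table 8 in Section 7.1.3.1 treats the surveillance cultures as laboratory tests: "surveillance Monitoring will include routine monitoring of CBC, CMP (including CRP, ESR) and blood cultures". Scheduled laboratory summaries in 8.5 are tied to infusions. Two further laboratory sentences there carry no time limit: "The incidence of clinically significant laboratory abnormalities will be presented", and "Laboratory data will be presented for patients having Grade 3 or 4 changes from baseline". Section 8 names no summary of surveillance results.

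**The concern.** The risk that the surveillance exists to detect arises, by its nature, after treatment has stopped. The AE rules close long before the first 4-monthly culture. If they are followed as written, the AE tables could show no listeria event even though a subject developed listeriosis a year after the last dose.

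At stake is the answer to a plain safety question about a live Listeria product: how many dosed subjects became infected over 3 years, how many were cultured at each visit, and how many were positive. Every dosed subject gives blood for 3 years to answer it, and the analysis section does not say that the answer will be reported.

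**Working it through.** The plan gives no figure to reproduce. The check compares calendar windows.

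**Inputs**

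- AE recording and AE summaries close at day 30 after the last dose (Section 6.1 footnote 9, 7.1.2.1, 7.2, 8.5). The safety telephone call at 30 ± 5 days (Section 7.1.6.3) could stretch this to day 35 at most.
- Surveillance draws are 4 months apart, ±14 days, for 36 months after the last dose (Sections 5.6.4 and 7.1.6.3).
- One month = 365.25/12 = 30.44 days.
- Assumption: the first draw is at month 4. The plan does not say so expressly.

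**Step 1: number and dates of draws.** 36/4 = 9 draws. Draw k falls at 4k × 30.44 days: about days 122, 244, 365, 487, 609, 730, 852, 974 and 1096.

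**Step 2: earliest permitted draw.** 122 − 14 = day 108.

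**Step 3: distance from the AE window.** 108 − 30 = 78 days, or 108 − 35 = 73 days with the telephone window. None of the nine draws falls inside.

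**Step 4: share of the surveillance period covered.** 30/1096 = 2.7% of the 36 months.

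**Step 5: apply the 8.5 rule.** The rule turns on onset date, not detection date. An infection found at the earliest month-4 draw would need an onset dated at least 78 days before the draw to qualify. Any listeriosis with onset after day 30 fails.

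**Step 6: trace the recording routes after day 30.**

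| Late listeriosis | Stated route | In the 8.5 AE tables? |
|---|---|---|
| Serious and judged related | Immediate report to the sponsor at any time (7.2.3.1) | No |
| Serious and judged unrelated | None after 30 days | No |
| Non-serious | None after 30 days | No |

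**Step 7: sensitivity to the assumptions.** A draw at the start of surveillance, if taken, could fall inside day 30, but the nine 4-monthly draws would stay outside. If surveillance is counted from a later discontinuation date, the draws move further from the last dose and the result is unchanged.

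**Step 8: why numbers cultured are needed.** With zero positives among n subjects cultured, the one-sided 95% upper limit is 1 − 0.05^(1/n). For n = 55, the planned total, this is about 5.3%. For n = 20, an assumed number still attending late visits, it is about 13.9%. The same zero means different things at different visits.

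**The case against.** The strongest reply is that little would really be lost. Section 7.2.3.1 has related SAEs reported whenever they surface. Section 5.6.4 requires intensive intravenous treatment of late listeriosis, so most cases would probably be serious and, after a live Listeria product, probably judged related. A positive culture is a clinically significant laboratory finding on a plain reading and could enter the laboratory summary, which has no time limit. Section 8.1 promises data listings, Section 8.4 provides internal review, Section 1 describes AE follow-up of at least 30 days, and table detail is left to a SAP.

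Much of this stands as a limit on the harm, but it does not close the gap. Reporting a case to the sponsor does not alter the onset rule in 8.5. A laboratory summary may show a positive culture, but it does not count an infection as an AE. At least 30 days is a floor with no later end date, while the operative sections give an end. A SAP can add a table, but it cannot tabulate non-serious or unrelated events that the protocol does not collect.

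Three stronger readings are tempting and are not supported:

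- A reader might infer that late infections would go untreated or unknown to the sponsor. Sections 5.6.4 and 7.2.3.1 say otherwise for treatment and for related SAEs.
- A reader might infer that recording of the 6-month antibiotic course also closes at day 30. The 30-day limit in Sections 5.5.1 and 7.1.1.6 is in the sentences on medications generally; the sentences on protocol-mandated antibiotics carry no limit of their own.
- A reader might infer that exactly one of the nine cultures is taken on antibiotics. That depends on which clock is used. Section 7.1.6.3 counts draws from the last dose, while Section 7.1.6.2 lets antibiotics start at discontinuation. A course of about 183 days started on day 47 would end on day 47 + 183 = 230, when the month-8 window opens (244 − 14 = 230); a later start would overlap it. The plan also does not claim that an early negative culture proves eradication.

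**Conclusion.** The concern holds for AE collection and the study-level safety summary. Under the stated rules, listeriosis with onset more than 30 days after the last dose is excluded from the AE tables, and a late case judged non-serious or unrelated has no stated recording route. All nine 4-monthly draws fall after the window, the nearest by 78 days, assuming the first is at month 4. An extra draw at the start of surveillance would not change that.

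Patient management and expedited reporting of related SAEs are not affected, and a positive culture may still appear among laboratory abnormalities. The primary efficacy analysis is untouched. The change should be made because the omission follows from a stated rule, not merely from missing detail, and because it concerns a safety criterion that the protocol itself names.

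**What to change.** In Section 8.5 add: *Listeria infections with onset at any time up to the end of Lm surveillance, including after the defined end of study, will be listed and counted regardless of the 30-day AE window, with the number of subjects cultured and the number positive at each surveillance visit.*

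In Section 6.1 footnote 9, Section 7.1.2.1 and Section 7.2 add: *Listeria infection events, serious or not and regardless of attribution, will be collected to the end of Lm surveillance.*

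The reference to the end of study is needed because Section 2 sets it at 1 year after the last enrolment. Even if the last subject received a single dose at about the time of enrolment, surveillance would run to about year 3, 3 − 1 = 2 years beyond that point. An addendum to the safety report would cover such subjects.

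The cost is longer collection of one event type at visits already scheduled, one small table and the addendum. Draws, visits and antibiotics do not change. Flagging cultures taken during the antibiotic course is optional.

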1 SUMMARY

Study Title:	Phase 2 Study of ADXS11-001 In Subjects with Persistent/Recurrent, Loco-Regional or Metastatic Squamous Cell Carcinoma of the Anorectal Canal
Trial Phase	Phase II
Clinical Indication	Persistent/recurrent, loco-regional or metastatic squamous cell carcinoma (SCCA) of the anorectal canal
Trial Type	Interventional
Study Centers	Multicenter, USA
Route of Administration	Intravenous (IV)
Trial Blinding	Open label, unblinded
Number of Trial Subjects	Approximately 55 
 • 31 subjects in Stage 1 • 24 subjects in Stage 2
Estimated Duration of Trial	Approximately 6 years
Duration of Participation	Each subject will participate in the study for an average of approximately 6 years from the time the subject signs the informed consent form (ICF) through the final contact. Treatment will continue for up to 2 years or until the subject meets a discontinuation criterion (e.g., has either documented progression, unacceptable adverse events (AEs), withdrawn due to investigator's discretion, subject withdraws consent, pregnancy, or noncompliance with study procedures or treatments). Subjects who have been on therapy for >6 months and who attain a complete response (CR) may consider stopping the trial. Subjects who achieve a CR should receive at least 1 additional cycle of treatment. The study duration includes an active study treatment phase which may last up to a maximum of 36 months and a 3 year Lm Surveillance Monitoring Phase, which includes 6 months of oral antibiotic administration to commence upon completion of the active study treatment phase or upon study discontinuation. All subjects will be followed for adverse and serious adverse events (SAEs) for a minimum of 30 days. End of Study will be defined as 1 year after the last subject is enrolled on study. However, any ongoing subject, subjects who are still deriving clinical benefit from ADXS11-001 therapy at the end of their 2 year treatment period or at the end of the study may be enrolled into a separate extension study, as available.
Randomization Ratio	None

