2 TRIAL DESIGN

Specific procedures to be performed during this trial, as well as the prescribed times and associated visit windows are outlined in the Schedule of Events- [Section 6.1](#). Details of each procedure are provided in [Section 7.1](#) - Trial Procedures.

This is a multi-center, open-label, 2 stage monotherapy study of ADXS11-001 in subjects with persistent/recurrent, loco-regional or metastatic SCCA of the anorectal canal that was previously treated in the metastatic setting. Stage 1 of the study will evaluate the safety and efficacy of ADXS11-001. After 31 evaluable subjects have been enrolled, further accrual will be temporarily stopped in Stage 1 to complete an interim efficacy

analysis evaluation. If the efficacy from Stage 1 demonstrates a response rate $\geq 10\%$ by either RECIST 1.1 or 6-month progression free survival (PFS) rate $\geq 20\%$, enrollment will re-open to Stage 2. Enrollment will be complete in Stage 2 when an additional 24 evaluable subjects have been accrued (total 55).

Subjects will be treated with intravenous (IV) ADXS11-001 administered over [REDACTED] every 3 weeks at a dose of 5×10^9 CFU for up to 2 years or until a discontinuation criterion is met. A treatment cycle is defined as 9 weeks. Tumor assessments will occur every 9 weeks (Week 8 of every Cycle). Subjects will be monitored for adverse events (AEs) throughout the study; AEs will be graded in severity according to the guidelines outlined in the NCI Common Toxicity Terminology Criteria for Adverse Events (CTCAE) version 4.0.

Safety follow-up will be conducted via telephone call 30 days (± 5 days) after the last ADXS11-001 infusion to confirm the resolution of any ongoing AEs and SAEs. Survival Follow-Up will be conducted at each visit during the Lm Surveillance period and via a telephone call every 3 months (± 2 weeks) after the Lm Surveillance period to determine survival status for all subjects.

The end of the study will be defined as 1 year after the last subject has enrolled on study. However, any ongoing subjects, subjects who are still deriving clinical benefit from ADXS11-001 therapy at the end of their 2-year treatment period or at the end of the study may be enrolled into a separate extension study, as available.

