5.8 Withdrawal/Discontinuation Criteria

Subjects may withdraw consent at any time for any reason or be dropped from the trial at the discretion of the investigator should any untoward effect occur. In addition, a subject may be withdrawn by the investigator or the Sponsor if enrollment into the trial is inappropriate, the trial plan is violated, or for administrative and/or other safety reasons. Specific details regarding discontinuation or withdrawal are provided in [Section 7.1.5](#).

A subject can be discontinued from the treatment for any of the following reasons:

- Screen Failure
 - Adverse Event/Serious Adverse Event
 - Lost to Follow-Up
 - Disease Progression, radiographic and/or clinical
 - Death
 - Withdrawal of Consent by Subject
 - Investigator Decision/Study Non-Compliance by Subject
-

- Achieved Complete Remission
- Completed Study (maximum 24 months of study treatment)
- Other (specify)

In all cases, the reason for and date of withdrawal must be recorded in the eCRF and in the patient's medical records. The patient must be followed up to establish whether the reason was an AE, and, if so, this must be reported.

When a subject discontinues/withdraws prior to treatment completion, all applicable activities scheduled for the final assessment (End of Therapy assessments) should be performed at the time of discontinuation. Any AEs that are present at the time of discontinuation/withdrawal should be followed in accordance with the safety requirements outlined in [Section 7.2](#).

The investigator must make every effort to contact subjects who discontinue the study prematurely or are lost to follow-up and to schedule the end of therapy assessments. Attempts to contact such subjects must be documented in the patient's records (e.g., times and dates of attempted telephone contact, receipt for sending a registered letter).

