7.1.6.3 Safety Follow-up/Post-Treatment Visits

Safety follow-up will be conducted via telephone call 30 days (± 5 days) after the last ADXS11-001 infusion to confirm the resolution of any ongoing AEs and SAEs. Additional unscheduled visits may be considered as needed and at the discretion of the investigator.

Surveillance monitoring for the detection of *Lm* will be initiated at the completion of study treatment according to the protocol or at the time of study discontinuation if earlier. This surveillance monitoring phase will consist of a 6 month course of oral antibiotics, obtaining a blood sample to monitor CBC, CMP, including CRP and ESR, and blood cultures at regular intervals. This testing will be performed on all subjects who have received at least one dose of ADXS11-001. It will occur every 4 months (± 2 weeks) for 3 years beginning after the last dose of study treatment. If a persistent increase in CRP and/or ESR is observed with negative blood cultures for listeria during this time the subject should be evaluated and treated, as appropriate, for another possible cause. In the event that a definite cause has not been identified then subjects must continue to be monitored closely, including another additional testing and a blood culture, for possible signs/symptoms of listeriosis. This testing may be performed at the investigative site or at another acceptable location following consultation with the Sponsor.

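### End of Study, set at 1 year after last enrolment, contradicts the 3 years of Lm surveillance required after the last dose in every dosed subject

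*Combined protocol and SAP*

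**What the plan says.** **Surveillance.** Section 5.6.4 sets out blood cultures, CBC and CMP with CRP and ESR every 4 months, within 2 weeks either side, for 3 years: "Testing will be performed on all subjects who have received at least one dose of ADXS11-001". Section 7.1.6.3 fixes the clock: "for 3 years beginning after the last dose of study treatment". Section 6.1 (footnote 13) and the notes to Table 8 repeat the schedule. A 6-month oral antibiotic course starts about 72 hours after the last dose.

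**Place in the study.** Section 1 counts the phase as part of the study: "The study duration includes an active study treatment phase which may last up to a maximum of 36 months and a 3 year" Lm surveillance phase. It also says "Each subject will participate in the study for an average of approximately 6 years", measured from consent to the final contact. Survival calls every 3 months follow the surveillance period (Sections 2, 6.1 footnote 5, 7.1.6.4), with no stated end.

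**End of Study.** Section 1: "End of Study will be defined as 1 year after the last subject is enrolled on study". Section 2: "The end of the study will be defined as 1 year after the last subject has enrolled on study". Both sections then allow ongoing or benefiting subjects to enter a separate extension study if one is available.

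**Treatment limit.** Sections 2, 5.8 and 7.1.5.1 cap treatment at 24 months. Section 1 gives both 2 years and a 36-month maximum.

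**The concern.** Three years counted from a subject's last dose cannot fit inside one year counted from the last enrolment, unless that subject stopped treatment well before accrual closed. A site that follows the End of Study sentence would close with surveillance unfinished. A site that follows Section 5.6.4 would be running mandatory visits after the protocol says the study has ended.

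What is at stake is scheduled culture and laboratory monitoring for delayed listeriosis, which Section 1 lists among the safety evaluations. Routine adverse event collection runs only "through 30 days after the last ADXS11-001 infusion is administered" (Section 6.1, footnote 9). After that, the surveillance visits are the only scheduled check for Lm. Subjects without symptoms, or with only a raised CRP or ESR, are the ones whom such visits exist to find, and they could go unmonitored for whatever visits fall after End of Study.

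**Working it through.** **Inputs**
- Visit interval 4 months, window 2 weeks (14 days, 0.46 months): Sections 5.6.4 and 7.1.6.3.
- Surveillance length 36 months from the last dose: Section 7.1.6.3.
- End of Study at 12 months after last enrolment: Sections 1 and 2.
- Treatment maximum 24 months (Sections 2, 5.8, 7.1.5.1); Section 1 also gives 36.
- Assumption: the first dose is on the day of enrolment. A later first dose can only lower the counts.

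**The plan's own duration.** 36 months of active phase + 36 months of surveillance = 72 months, which reproduces the 6 years in Section 1. With the 24-month limit, 24 + 36 = 60 months, or 5 years to the end of surveillance.

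**Number of visits.** 36 / 4 = 9. The documents do not state this count; it follows from the schedule.

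**Last-enrolled subject.** Let d be months from enrolment to last dose. Visit k, taken as early as its window allows, is inside the study if d + 4k − 0.46 ≤ 12.

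| d (months) | Last visit inside | Next visit | Visits in study |
|---|---|---|---|
| 0 (single dose) | k=3 at 11.54 | k=4 at 15.54 | 3 of 9 |
| 1.4 (one full cycle, last dose day 43) | k=2 at 8.94 | k=3 at 12.94 | 2 of 9 |
| 6 | k=1 at 9.54 | k=2 at 13.54 | 1 of 9 |
| more than 12 − 4 + 0.46 = 8.46 | none | k=1 after 12 | 0 of 9 |

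**Sensitivity of the best case.**
- If each visit is counted from the previous one and always taken early, visit 4 falls at 4 × (4 − 0.46) = 14.16 months, so the maximum stays at 3.
- With 28 days (0.92 months) from enrolment to first dose, visit 3 falls at 0.92 + 12 − 0.46 = 12.46 months, and the maximum drops to 2.
- If a test at the very start of surveillance were also counted, the best case would be 4 of 10. The conflict remains.

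**Any subject.** To finish, last dose + 36 − 0.46 ≤ last enrolment + 12. The last dose must therefore come at least 36 − 0.46 − 12 = 23.54 months, about 23.5, before last enrolment. Adding time on drug gives the enrolment cut-off before the end of accrual: 23.5 months for a single dose, 23.5 + 1.4 = 24.9 for one cycle, and 23.5 + 24 = 47.5 for full treatment.

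**Antibiotic course, last-enrolled subject.** It ends at about d + 0.1 + 6 months, so it runs past End of Study when d > 12 − 6.1 = 5.9. If the subject is still on drug at End of Study, the whole course falls after it.

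**End of Study needed** for the last-enrolled subject to reach the nominal ninth visit: 36 months after last enrolment for a single dose, and 24 + 36 = 60 months after full treatment, against 12 stated.

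**The case against.** The strongest reply is that nothing says surveillance stops at End of Study. The surveillance instructions are specific and unconditional, and the roughly 6 years of participation in Section 1 shows that completion is intended. This stands. A reader might infer that late subjects will go unmonitored, but the documents support only that they could. The defect is an End of Study sentence that contradicts the surveillance requirement, not a decision to cut surveillance short.

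The extension study does not close the gap. Entry is optional and depends on availability. Section 7.1.5.1 describes it for subjects still benefiting at 2 years, or who progress within a year of stopping after a complete response. No section says that it carries Lm surveillance. Nor does any section describe the 1-year date as merely an efficacy data cutoff.

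A reader might also infer that the 6-year average must be wrong because it equals the sum of two maxima. That is not shown: participation runs to the final contact, and survival calls continue after surveillance without a stated end.

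Recognised serious cases are not lost. Section 7.2.3.1 keeps related serious adverse events reportable at any time once the investigator learns of them, and Section 5.6.4 requires education on delayed listeriosis.

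Finally, the number of subjects affected is unknown. No accrual time is given, and Section 4.2.2.1 describes a poor long-term prognosis, so some subjects will die before the visits in question. No cohort percentage is claimed.

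**Conclusion.** The point holds as an internal contradiction in a safety-relevant rule. As written, the last-enrolled subject can have at most 3 of the 9 surveillance visits before End of Study, and none if the last dose is more than about 8.5 months after enrolment. Any subject whose last dose falls less than about 23.5 months before last enrolment cannot complete surveillance by that date. These are calendar results. They rest on dosing at enrolment and use of the early side of the 2-week window, both of which favour the plan, and they apply to subjects who survive and remain in follow-up. The consequence is that scheduled monitoring and part of the antibiotic course could be left without protocol cover; it is not shown that they would be omitted. The definition should be corrected.

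**What to change.** In Sections 1 and 2, define End of Study as the date on which the last subject completes the 36-month Lm surveillance visit, or dies, withdraws or is lost before it. State that post-surveillance survival calls for the other subjects continue until that date. Without this, Sections 2, 6.1 (footnote 5) and 7.1.6.4 would still require calls after End of Study.

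Alternatively, keep the present End of Study date and require transfer of all dosed subjects to a surveillance follow-up protocol.

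In Section 1, replace the 36-month treatment maximum with the 24 months used in Sections 2, 5.8 and 7.1.5.1. Update the participation figure to match (up to 24 + 36 = 60 months per subject to the end of surveillance), and set the estimated trial duration to that figure plus accrual.

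Cost: no added subjects and no visits beyond those already required. The study stays open at low activity for up to 24 + 36 − 12 = 48 months past the current End of Study date, and the last subject to finish surveillance would have no survival calls after it. The transfer option lets this study close on its present date but needs a second protocol.
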